
D2. Study Population & Eligibility Criteria

The study will be based at the ambulatory obstetrical practices of Baystate Medical Center, a large tertiary care facility in Western Massachusetts that serves a socioeconomically diverse population; 4,300 infants are delivered annually, 57% are Hispanic (predominantly from Puerto Rico with ~58% having income <\$15,000 per year). Eligible women will be Hispanic, overweight or obese (BMI >25 kg/m²), and 16-45 years of age. We will exclude women with 1) prepregnancy BMI <25 kg/m², 2) history of type 2 diabetes, heart disease, or chronic renal disease, 2) contraindications to participation in moderate physical activity or to a low-fat/high-fiber diet (e.g., Crohn's disease, ulcerative colitis), 3) inability to read English or Spanish at a 6th grade level, 4) <16 or >45 yrs of age, 5) >20 wks gestation, 6) current medications which adversely influence glucose tolerance, 7) not planning to continue to term or deliver at the study site, or 8) pregnant with twins or triplets. Women who have a very early preterm birth (<34 wks), a miscarriage, or a still birth after enrollment or a stillbirth will be excluded. Women who become pregnant again in the year following delivery will be censored at the time of their positive pregnancy test.

D3. Recruitment, Baseline Assessment, and Sample Size

Bilingual (Spanish and English) and bicultural health educators will recruit women at the first prenatal care visit (~10 wks gestation). Women will be informed of the aims/procedures of the project, sign an informed

consent, and complete a screening form to determine eligibility. The baseline assessment will be collected via standardized questionnaire and the pregnancy blood sample will be taken (see Figure 1). Expectations for the study and a contacts schedule (face-to-face meeting, mailings, booster telephone calls) will be reviewed. Each assessment and interview completed is associated with a gift card for a total of up to \$360, to be handed out after completing the study component.

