To ensure retention and to control for contact time, the Comparison Health & Wellness arm receives mailed materials and telephone booster calls on the same schedule as the Lifestyle Intervention arm (Figure 1). In this way, we control for contact time, while keeping the content of the two interventions distinct. These booklets represent high-quality, standard, low-cost, self-help material currently available to the public which focus on non-exercise and non-dietary topics in both English and Spanish. These include the ACOG series of informational booklets on general issues related to health and wellness during pregnancy (e.g., Alcohol and Drug Use during Pregnancy, Easing Back Pain) and the American Academy of Pediatrics booklets on parent resources (e.g., Parenting your Infant). Hispanic control-arm participants in our prior studies (R01DK074876, R01NR011295, R21NR009864) reported that these materials were of interest¹⁴⁹ and differential dropout did not occur between study arms.

D.12. Outcome Variables

D.12.1. Biomarkers of Insulin Resistance and Other CVD Risk Factors

Fasting samples will be collected at a Baystate Reference Laboratory at baseline (~10 weeks gestation), 24-28 wks, and 32-34 wks gestation during routine prenatal care visits, and at 6 wks, 6 mos, and 1 yr, and among children at ~1 yr postpartum (coordinated with timing of the routine lead/CBC screen) (termed “blood draw”). Samples will be stored at -80 degrees Celsius in a freezer at Baystate with temperature monitoring, alarm and a back-up power system. Samples will be shipped periodically to the assaying lab. Residual blood samples will be stored at [name] lab to resolve potential data validation questions related to this study, and will be destroyed 7 years after study completion, unless the participant agrees to storage for future studies (included as “opt-in” in the informed consent form). Quality control for specimen handling will be performed monthly by the head lab technician. Samples will be assayed by [name] (Department of Laboratory Medicine, Harvard University) at Children’s Hospital, Boston, MA.

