Recruitment, health education, and telephone assessments will be conducted by trained bilingual (English/Spanish) health educators and assessors. We have built a training course based upon staff feedback and quality control during previous studies (Estudio PARTO, The B.A.B.Y Study and Estudio VIDA) with an accompanying manual which includes instruction on motivational interviewing techniques, role-playing, specific study protocols and scripts. Regular quality assurance and quality control reviews will include observations of the health educator. The observations will be done by asking participants permission to audio record a contact. The recordings will be scheduled so that the same day as the contact, the study coordinator will be available to review the interaction with the health educator, assess the quality of the interaction, and use the time as an opportunity to re-train the health educator as necessary. Assessors will be monitored in the same way. The audio recordings will be (audibly) identified with the participant's study ID and contain no PHI. The recordings will be destroyed once they are reviewed. When not in use, the recorder/memory card will be kept in a locked container in a locked room at Baystate. If a staff person is observed departing from standard protocol, feedback and recommendations for retraining will be provided. The assessor will be blinded to the treatment assignment. The health educator will be blinded to the results of the assessor's assessments. The medical record abstractor will be trained using the Medical Record Abstraction Manual and training program developed as part of our prior studies. The medical record abstractor will be blinded to the treatment assignment.

Our research group has had extensive experience with Baystate medical records over the past 12 years. We have systematically assessed the records for organization as well as completeness through correlations with the hard copy medical record systems and the billing database. Key variables for abstraction have been found to be accurately reported on the electronic system. Reliability of medical record abstraction will be assessed by abstraction of 10% of the medical records twice. The abstractor will be retrained based upon the findings from this assessment. Monthly staff meetings will be attended by the telephone assessor, health educator, medical record abstractor, data analyst, laboratory technician, Project Manager and the Principal Investigator.

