Specific Aim #1, 2, 3: Impact of a Lifestyle Intervention on GWG and postpartum weight loss; biomarkers of insulin resistance; postpartum biomarkers of CVD risk. The primary analysis will evaluate differences in the change from baseline in weight gain measures, glycemia and other biomarkers of insulin resistance and cardiovascular risk factors between the groups (an intent to treat analysis). Initial analyses will describe the correlation of factors and investigate simple transformations for normality. The primary analysis will be based on a mixed model with random subject effects, including a common mean at baseline for the intervention groups, a period effect, and an intervention by period interaction.¹⁷⁰ The intervention by period interaction is a measure of the intervention effect, and corresponds to the estimate of an intervention effect in an analysis of covariance. The mixed model analysis will enable inclusion of time varying covariates such as depression, breastfeeding behaviors, and sleep, which may vary between baseline and follow-up for subjects. Equivalence of the intervention groups will be assessed by comparing the distribution of the potential confounders between each group. We will investigate established risk factors for weight gain (e.g., parity) and glycemia as well as degree and treatment for abnormality on glucose tolerance testing during pregnancy (e.g., diet, oral hypoglycemic and/or insulin) as potential confounders or effect modifiers. Generally, we will consider a change in the parameter estimate for the exposure (at least 15%), relative to that observed when not controlling for the variable as reflective of confounding. Effect modification will be evaluated by inspection of stratum specific odds ratios as well as by evaluating the statistical significance of interaction terms via likelihood ratio tests. We will also model the relationship between measured levels of exercise, sedentary behavior, and diet with each outcome, while adjusting for possible confounders using mixed effect linear regression models. We will test hypotheses with 2-sided tests. Finally, we will compare adoption and maintenance of behavior change (i.e., exercise, diet) in the intervention group relative to the control group by adding a fixed treatment group effect.

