Specific Aim #4: Evaluate the impact of a Lifestyle Intervention on the outcomes of offspring. We will evaluate the impact of intervention arm on the offspring outcomes using the methods described for Aim #1-3. We will also examine GWG and prenatal glycemic factors as predictors of glycemia and weight gain in early infancy and childhood. Important covariates are listed in the covariate section. In models focused on offspring weight gain as the outcome, we will additionally adjust for fetal growth (i.e., BW/GA z score).

Specific Aim #5: Evaluate the cost-effectiveness of the Lifestyle Intervention. We will use procedures developed in our prior studies examining the cost-effectiveness of our interventions.¹⁷¹⁻¹⁷³ We will calculate the ratio of average dollars spent per average incremental improvement in outcome (i.e., GWG, postpartum weight retention, and biomarkers of insulin resistance and CVD risk). Incremental improvement will be defined as the mean change score from baseline for each group, adjusted for baseline values of the outcome measure and other participant characteristics.

Accounting for Missing Data: Although every effort is made to avoid missing data, we plan to use propensity score techniques¹⁷⁴⁻¹⁷⁶ to evaluate the potential sensitivity of results to missing at random assumptions. Multiple comparisons will be addressed by carefully considering the biologic rationale of observed associations.

D.17. Power

To achieve power to detect clinically significant differences requires 300 participants (150 in each intervention arm) at the time of delivery. Based on observed rates in our 2 trials (R01DK074876 and

ASPH/CDC S3948), we conservatively expect 10% of women to leave the New England area, deliver elsewhere, or withdraw during pregnancy, and therefore will recruit 333 women over the 24 mos recruitment period. For offspring outcomes, we calculate that 4% will be excluded for very early preterm birth (<34 wks), miscarriage, or stillbirth resulting in 288 children at delivery. Over the following 1 yr, we conservatively project that an additional 8% of women will be lost to follow-up due to withdrawal or movement out of the New England area. Women who become pregnant again will be censored. Therefore, we expect 264 women and children at 1 yr postpartum.

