Prior to randomization (~12 wks gestation), and again after delivery, participants will fill out the Physical Activity Readiness Questionnaire. If they answer yes to any of the questions on the questionnaire, [name] (Co-Investigator, and Director of Maternal/Fetal Medicine at Baystate) will evaluate the participant for study inclusion by reviewing prenatal visit records, the delivery medical records, and/or postpartum visit records. It is important to note that we conservatively scheduled the onset of the Intervention Postpartum Phase to not begin until 6 weeks postpartum, a time by which the physiologic and morphologic changes of pregnancy no longer persist for the majority of women (ACOG Committee opinion. January 2002: “Exercise during Pregnancy and the Postpartum Period”). The American College of Obstetricians and Gynecologists recommends that, in the absence of complications from delivery, a mild exercise program consisting of walking, pelvic floor exercises, and light stretching of all muscle groups can begin in the immediate postpartum period (ACOG Committee opinion. January 2002: “Exercise during Pregnancy and the Postpartum Period”). A similar recommendation was made by ACOG for exercise during pregnancy (during the Intervention Pregnancy Phase). In the case that [name] determines there are contraindications to the lifestyle intervention, the woman will be excluded from the study and immediately contacted by the Project Coordinator by telephone and in writing.

Although the likelihood is low, our research team has well-established procedures for monitoring and responding to adverse events resulting from moderate intensity physical activity. First, during the orientation participants will be provided with contact information for study personnel and instructed to contact our team if any exercise related adverse event occurs (e.g., soft tissue injury). Additionally, we will be corresponding with the study participants over brief time periods to obtain study-related questionnaires. As part of those questionnaires, participants will be asked whether any adverse event occurred. In the case of any report, the Principal Investigator will be immediately notified, who will then notify the DSMB and Institutional Review Board. In cases of injuries that interfered with functioning (i.e., ability to move about), the participant will be asked to cease activity and obtain physician clearance before continuing.

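### The activity screen repeated after delivery would exclude women already randomised, ending their postpartum follow-up for a reason tied to one arm's intervention

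*Combined protocol and SAP*

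**What the plan says.** In E.2, under Protection Against Risk, the screen is given twice to participants in both arms: "Prior to randomization (~12 wks gestation), and again after delivery, participants will fill out the Physical Activity Readiness Questionnaire". Any positive answer sends the case to a co-investigator, who decides on the woman's inclusion from prenatal records, delivery records, postpartum records or a combination. If that reviewer finds contraindications to the lifestyle intervention, "the woman will be excluded from the study and immediately contacted by the Project Coordinator by telephone and in writing".

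The next paragraph of E.2 treats injuries that limit functioning differently: "the participant will be asked to cease activity and obtain physician clearance before continuing".

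Other sections that bear on this:

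- **D.5 (Randomization)** describes one check only, immediately before randomisation at about 12 weeks. It consists of a single question on whether the woman's provider has restricted her activity.
- **D2 (Eligibility)** lists contraindications to moderate activity among the entry criteria. Its separate sentence on exclusions after enrolment reads: "Women who have a very early preterm birth (<34 wks), a miscarriage, or a still birth after enrollment or a stillbirth will be excluded".
- **D.16 (Statistical Analysis)** compares changes in weight, insulin-resistance biomarkers and "cardiovascular risk factors between the groups (an intent to treat analysis").
- **D.17 (Power)** allows for loss in the postpartum year as follows: "an additional 8% of women will be lost to follow-up due to withdrawal or movement out of the New England area".
- **D.11** says the control booklets "focus on non-exercise and non-dietary topics in both English and Spanish".
- **D.14** states blinding for the assessor and adds: "The medical record abstractor will be blinded to the treatment assignment". It says nothing about the co-investigator who reviews contraindications.

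**The concern.** Randomisation takes place at about 12 weeks and the second screen after delivery, roughly six months later at term. A rule that removes women at the second screen is therefore an exclusion after randomisation, based on a condition that arises during follow-up. It sits badly with an intent-to-treat analysis, and the plan does not say whether data already collected from these women are kept.

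The reason for leaving is fitness for one arm's intervention. Control women are not offered that intervention, so the finding gives them no safety reason to go. In neither arm does a contraindication to exercise make weighing or blood sampling unsafe.

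What is at stake is the postpartum half of the trial: postpartum weight loss (Aim 1) and the postpartum biomarkers (Aims 2 and 3) measured after the exclusion. Missingness would differ by arm if the intervention changes who has a contraindication after delivery, or if the reviewing physician knows the arm. The plan does not say that this reviewer is blinded.

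**Working it through.** **1. Does the exclusion rule reach randomised women?**

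The exclusion sentence carries no date, so its scope has to come from its surroundings.

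- The paragraph opens by naming two screens, one before randomisation and one after delivery.
- The records to be reviewed include those of the delivery and of postpartum visits. For this pregnancy they cannot inform a decision at about 12 weeks, so the review must also operate after delivery.
- The exclusion follows from that review, without limit of time or arm.
- The injury rule in the next paragraph shows how the authors write when they mean only that activity should stop. They used stronger words for contraindications.
- E.1 (Sources of Materials) rules out exclusion for noncompliance. It does not cover a medical contraindication.

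The natural reading is that the rule covers women already randomised. Neither the post-enrolment exclusions in D2 nor the attrition allowances in D.17 mention it.

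**2. The plan's own figures (D.17 and Table 3)**

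- Attrition: 333 × 0.90 = 299.7 (stated 300); 300 × 0.96 = 288 (stated 288); 288 × 0.92 = 264.96 (stated 264).
- Detectable difference in postpartum weight loss, with N = 264, SD = 6, two-sided 5% and 80% power: SD × (1.960 + 0.842) × √(4/N) = 6 × 2.802 × 0.1231 = 2.07 kg (stated 2.1).

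These reproduce to rounding.

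**3. Number of women affected**

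The documents give no rate of contraindication after delivery. I assume 2–5% of the 288 who remain after the 4% exclusions:

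- 288 × 0.02 = 5.8
- 288 × 0.05 = 14.4

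That is about 6 to 14 women.

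**4. Power for 2.1 kg, SD 6 (normal approximation)**

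Power = Φ(2.1 / (6 × √(2/n)) − 1.96), with n per arm.

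| Further loss (assumed) | Total N | Power |
|---|---|---|
| 0% | 264 | Φ(0.883) = 81% |
| 2% | 258.7 | 80% |
| 5% | 250.8 | Φ(0.811) = 79% |
| 10% | 237.6 | 77% |

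**5. Possible bias**

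If a fraction f of an arm is removed and these women differ from those retained by D kg, the mean of the retained women differs from the full-arm mean by f × D. With the same D in both arms, a comparison of the remaining women shifts by (f₁ − f₂) × D.

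- Equal fractions: zero.
- 5% versus 2%, D = 3 kg (0.5 SD): 0.03 × 3 = 0.09 kg, and 0.09 / 2.1 = 4.3% of the detectable difference.
- 5% versus 2%, D = 6 kg (1 SD): 0.03 × 6 = 0.18 kg, and 0.18 / 2.1 = 8.6%.

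The fractions and D are all assumed.

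**The case against.** The strongest reply is that the sentence is undated and may be meant for entry only. D2 already makes a contraindication to activity an entry criterion, and D.5 places the inclusion review just before randomisation. On that view the screen after delivery is only clearance before the postpartum phase begins at 6 weeks. Section E also shows signs of text from another design: it describes recruitment at the time of gestational diabetes screening and a population with abnormal glucose tolerance, neither of which matches D2 and D3. A narrower intent is therefore possible. But the words do not express it, and staff following E.2 as written would remove these women.

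Second, stopping follow-up creates missing data; it breaks intent to treat outright only if women or their data are dropped from the analysis. That is a fair distinction, and the plan is silent on it. For a repeat pregnancy D2 does give a rule (censoring at the positive test); here there is none.

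Third, the shift in step 5 compares women who remain, whereas D.16 plans a mixed model that can use earlier measurements, and D.17's preceding paragraph on missing data adds propensity-score sensitivity analyses. This stands: 0.09–0.18 kg is not the bias of the planned estimate. Those methods can reduce the problem but do not recover outcomes that were never measured, and they do not remove the effect of informative missingness.

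Fourth, every driver of the size is assumed, the rule as written applies equally to both arms, and no text says the reviewer knows the arm. All of this is true, and it limits how much weight the numbers can bear.

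**Conclusion.** The concern holds. Read naturally, E.2 ends the postpartum follow-up of randomised women in both arms because of a contraindication to one arm's intervention. That is at odds with the intent-to-treat aim in D.16 and is not provided for in D2 or D.17.

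The likely numerical effect is small. At the assumed 2–5%, about 6–14 women lose later postpartum outcomes and power drops by at most about 2 percentage points. Bias is about zero if exclusions are alike in both arms, and 4–9% of the 2.1 kg detectable difference under the assumed imbalance in a comparison of those remaining. Gestational weight gain and pregnancy biomarkers are not affected. The case for changing the rule is that the loss is avoidable and serves no safety purpose that stopping the activity would not serve. Confidence is medium, because the exclusion sentence is undated and a narrower intent cannot be ruled out. The plan should be amended, but the point does not threaten the trial.

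A secondary wording point: D.5 and E.2 describe the screen before randomisation differently, one as a single question and the other as a full questionnaire. Both could apply, but the plan does not say so.

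**What to change.** In E.2, limit exclusion from the study to the screen before randomisation. For the screen after delivery, say that a contraindication only pauses or modifies the activity component, as E.2 already does for injuries, and that the woman stays in all assessments and in the intent-to-treat analysis in her allocated arm. In D.5 and E.2, describe one screening procedure before randomisation, or state that both the provider-restriction question and the questionnaire apply.

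The cost is protocol wording. No visit or procedure is added, and the safety protection is unchanged. If the sponsor always meant the narrower rule, one sentence settles it.
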